## 6.4.4 Device Deficiency reporting

The Investigator is responsible for recording the following in the CRF for all device deficiencies:

- Device deficiency details (e. g. date and description of occurrence).
- Whether the device deficiency led or could have led to an SADE.

For device deficiencies that fulfil the SADE definition the Investigator must provide Dentsply Sirona Implants with additional information.

### 6.4.5 Safety event follow-up

Medical follow-up of any type of safety event will continue until the abnormality resolves, or an adequate medical explanation is apparent.

Documentation of all follow-up information regarding the AEs must be provided in the CRF and, in accordance to the reporting requirements described above.

If it is suspected that the medical device under investigation may have interfered with the effectiveness of a contraceptive medication/device, this should be reported as an ADE. Pregnancy itself, or elective abortions without complications, should not be reported as AEs.

If the subject is withdrawn from study treatment due to an AE, the AE and the reason for withdrawal from the study is to be documented clearly in the CRF.

# 7 General study management

Study start is not allowed before all of the necessary approval documents (IEC/IRB approval, signed CIP, signed CSA, regulatory approval if applicable) are available and the study site has been initiated by Dentsply Sirona Implants.

## 7.1 Changes to the Clinical Investigation Plan (CIP)

Study procedures will not be changed without the mutual agreement of the coordinating Investigator and Dentsply Sirona Implants. If it is necessary for the CIP to be amended, the amendment and/or a new version of the CIP (Substantial Amendment) must be notified to or approved by each IEC/IRB, and if applicable, also the local Regulatory Authority, before implementation. Local requirements must be followed. If a CIP amendment requires a change to a particular study site's ICF, then Dentsply Sirona Implants and the study site's IEC/IRB must be notified. Approval of the revised ICF by Dentsply Sirona Implants and by the IEC/IRB is required before the revised form is used. Dentsply Sirona Implants will distribute amendments and new versions of the CIP to each PI(s), who in turn is responsible for the distribution of these documents to his or her IEC/IRB, and to the staff at his or her study site. The distribution of these documents to the Regulatory Authority will be handled according to local practice.

In general, a Non-substantial Amendment does not require a notification to or approval by IEC/IRB.

## 7.2 Monitoring

Before the first subject enters the study, a representative of Dentsply Sirona Implants will visit the study site to:

- Determine the adequacy of the facilities
- Discuss with the Investigator(s) (and other personnel involved in the study) their responsibilities with regard to CIP adherence, and the responsibilities of Dentsply Sirona Implants or its representatives.

During the course of the study, a study monitor from Dentsply Sirona Implants or representative will have regular contacts with the study site, including visits to:

- Provide information and support to the Investigator(s)
- Confirm that facilities remain acceptable
- Confirm that the investigational team is adhering to the CIP, that data are being accurately recorded in the CRFs, and that Investigational Product (IP) accountability checks are being

#### performed

 Perform source data verification (a comparison of the data in the CRFs with the subject's medical records at the hospital or practice, and other records relevant to the study). This will require direct access to all original records for each subject.

The study monitor or another Dentsply Sirona Implants representative will be available between visits if the Investigator(s) or other staff at the study site needs information and advice.

## 7.3 Audits and inspections

Authorized representatives of Dentsply Sirona Implants, a Regulatory Authority, an IEC/IRB may visit the study site to perform audits or inspections, including source data verification. The purpose of a Dentsply Sirona Implants audit or inspection is to systematically and independently examine all study-related activities and documents to determine whether these activities were conducted, and data were recorded, analyzed, and accurately reported according to the CIP, ISO 14155 and any applicable regulatory requirements. The Investigator should contact Dentsply Sirona Implants immediately if contacted by a regulatory agency about an inspection at his or her site.

# 7.4 Training of study site staff

The PI must maintain a record of all individuals involved in the study (medical, nursing and other staff), i.e. a Responsibility and Signature Log. He or she shall ensure that appropriate training relevant to the study is given to all of these staff, and that any new information of relevance to the performance of this study is forwarded to the staff involved.

Before the first subject is entered into the study, the study staff will be trained to use the EDC system by Dentsply Sirona Implants personnel or delegates.

## 7.5 Deviations from the Clinical Investigational Plan

The Investigator is not allowed to deviate from the CIP except in emergency situations, with purpose to protect a subject's rights, safety and wellbeing.

In such cases, the Investigator may proceed without prior approval of Dentsply Sirona Implants and the IEC/IRB. Furthermore, such deviations shall be documented and reported as soon as possible to Dentsply Sirona Implants and the IEC/IRB.

All CIP deviations must be directly reported to the Study Team Leader, by either the Investigator or Monitor. The further procedure of CIP deviation handling, with special focus on the effect on the data analysis is described in section 10.2 Description of analysis sets.

Should the Investigator break any obligations under the CIP or CSA and fail to remedy such a breach where it is capable of cure, Dentsply Sirona Implants retains the right to disqualify the study site from further study participation.

# 7.6 Study agreements

The PI at the study site should comply with all the terms, conditions, and obligations of the CSA for this study. In the event of any inconsistency between this CIP and the CSA, the terms of CIP shall prevail with respect to the conduct of the study and the treatment of subjects and in all other respects, not relating to study conduct or treatment of subjects, the terms of the CSA shall prevail.

Agreements between Dentsply Sirona Implants and the PI should be in place before any study-related procedures can take place, or subjects are enrolled.

# 7.7 Early termination of the study

The end of the study is defined as 'the last visit of the last subject undergoing the study'.

The study may be terminated at individual study sites if the study procedures are not being performed according to regulations (Declaration of Helsinki, ISO 14155 and applicable regulatory requirements) or if recruitment is slow. Dentsply Sirona Implants may also terminate the entire study prematurely if concerns for safety arise within this study or in any other study with the Investigational Product (IP).

# 7.8 Publication policy

Results from 1, 3 and 5-year data are planned to be compiled into e.g. manuscripts for submission to peer-reviewed scientific journals, poster presentations, oral presentations etc.

The data will be provided by Dentsply Sirona Implants and the writing process will be coordinated by the International Coordinating Investigator.

For authorship, see CSA.

# 8 Investigational Products (IPs)

Investigational Products are the Conometric Abutment and the Conometric Final Cap. Additional products are described below.

#### Investigational Products – for Ankylos

Product name Conometric Abutment

Diameter 3.3, 4.5 mm Heights 1.5, 3.0, 4,5 mm

Characteristics Straight or Angled 15°, Titanium Alloy-ELI

Straight 3.3 mm is an one-piece abutment

Product name Conometric Final Cap

Diameter 4.6, 5.8 mm Heights 5 mm

Characteristics Titanium grade 4, TiN-coated

### Additional Products - for Ankylos

Product name Ankylos C/X

Diameter 3.5, 4.5, 5.5, 7.0 mm

Lengths 6.6-17 mm
Characteristics Dental implants

Product name Conometric Healing Cap

Diameter 4.8, 6.0 mm
Heights 5.3 mm
Characteristics PEEK

Product name Conometric Temporization Cap

Diameter 4.6, 5.8 mm Heights 5, 5.3 mm

Characteristics Titanium Alloy-ELI/PEEK or PEEK

**Investigational Products – for Astra Tech Implant System** 

Product name Conometric Abutment

Diameter 3.3, 4.5 mm Heights 1.0, 2.0, 3.0 mm

Characteristics Straight or Angled 15°, Titanium Alloy-ELI

Straight 3.3 mm is an one-piece abutment

Product name Conometric Final Cap

Diameter 4.6, 5.8 mm Heights 5.0 mm

Characteristics Titanium grade 4, TiN-coated

Additional Products - for Astra Tech Implant System

Diameter 3.6 S, 4.2 S, 4.2 C mm

Lengths 6-17 mm

Characteristics Dental implants

Product name Conometric Healing Cap

Diameter 4.8, 6.0 mm
Heights 5.3 mm
Characteristics PEEK

Product name Conometric Temporization Cap

Diameter 4.6, 5.8 mm Heights 5.0, 5.3 mm

Characteristics Titanium Alloy-ELI/PEEK or PEEK

**Investigational Products – for Xive** 

Product name Conometric Abutment

Diameter 4.5 mm

Heights 1.0, 2.0, 3.0. mm

Characteristics Straight or Angled 15°, Titanium Alloy-ELI

Product name Conometric Final Cap

Diameter 5.8 mm Heights 5.0 mm

Characteristics Titanium grade 4, TiN-coated

#### Additional Products - for Xive

Product name Xive S plus
Diameter 3.4, 3.8 mm
Lengths 8-18 mm

Characteristics Dental implants

Product name Conometric Healing Cap

Diameter 6.0 mm
Heights 5.3 mm
Characteristics PEEK

Product name Conometric Temporization Cap

Diameter 5.8 mm
Heights 5.3 mm
Characteristics PEEK

### 8.1 Indications for use

The investigational products listed above are to be used in accordance with the Acuris – conometric concept for Dentsply Sirona implant systems; Ankylos, Astra Tech Implant System and Xive, i.e. an implant-prosthetic procedure for the restoration of single-tooth implants. The Conometric Abutments are intended to be used for fixed friction retained single crowns. Applicable Manuals for each category of investigational products and corresponding procedures shall be followed (manuals listed continuously in the text in the sequence they appear in the treatment flow).

## 8.2 Labeling

The packing and labeling of the Investigational Product will be performed by Dentsply Sirona Implants in accordance with GMP (Good Manufacturing Practice). The Labeling of the investigational product will also be carried out by Dentsply Sirona Implants in accordance ISO 14155. The labels will be available in English language and in accordance with local regulations.

In addition, study products will be labeled as follows:

- C-OT-17-003
- Name and address of Principal Investigator
- A separate label with text, according to national law in the country where the study is conducted, with the following sentence translated into local languages: "Only for clinical research".

# 8.3 Storage and accountability records

All Investigational Products (IP) must be kept in a dry and secure (locked) area. IP will be used only for this study and only in accordance with the CIP.

The PI is responsible for maintaining accurate records (Device Accountability Form) of the dispensing of IPs. Any IPs accidentally or deliberately destroyed must be accounted for and discrepancies between amounts dispensed and returned should be explained. All unused IPs must be returned to Dentsply Sirona Implants when treatment of the last subject has been completed.

# 9 Data collection and data management

## 9.1 Case Report Form recording and processing

Study data will be entered into electronic Case Report Forms (eCRFs) using Viedoc™, a web based Electronic Data Capture (EDC) system. Viedoc is compliant with good practices and regulatory requirements for clinical trials issued by e.g. FDA, EMA and PMDA. Trained and authorized study site personnel will be responsible for entering the study data into Viedoc. Data entered into Viedoc will be immediately saved to a central database, hosted by a 3rd party, PCG Solutions AB. Instructions for handling the system and filling in the eCRF e.g. how to log on, navigate and signing of data is found in the Investigator's Manual.

Dentsply Sirona Implants will review entered data, verify source data and lock data to prevent further editing. If not already done, the PI will be prompted to sign the eCRF electronically. A contemporaneous copy of the CRF will be available for the study site in Viedoc.

Data queries will be raised for inconsistent, missing, unclear or questionable data. The study site personnel is required to resolve any such queries. All entries in the study database will be available in an audit trail. When data is complete and clean, clean file will be declared. Any treatment revealing data may thereafter be added and the database will be locked.

## 9.2 Storage of data

Readable copies of the eCRF data, stored on a durable media e.g CD-ROM or DVD to be archived in the ISF at the study site after clean file. The copies will be created by trained study site personnel. Dentsply Sirona Implants will not at any time point be in control of the eCRF data archived in the ISF, unless the copy is sealed by 3rd party and then only for the purpose of delivering it to the study site.

Dentsply Sirona Implants will assume responsibility for the long-term storage of all data in compliance with the applicable local laws and ISO 14155. Study data will be securely stored at Dentsply Sirona Implants, with restricted access. Data will be retained by Dentsply Sirona Implants at least 15 years after this study has ended, or at least 15 years after the investigational devices are no longer available on any market, whichever is the longest.

# 10 Statistical methods and data analysis

## 10.1 Statistical evaluation – general aspects

A separate Statistical Analysis Plan may be prepared before database lock When using the terminology descriptive statistics it is meant that the number of subjects (N), mean, median, standard deviation (SD), minimum (min) and maximum (max) values will be presented for continuous data and frequencies and percentages for categorical data. If nothing else is stated, descriptive statistics will be given for each variable in the study and p-values may be complemented by confidence intervals as appropriate.

# 10.1.1 Demographics and other baseline characteristics

Demographics and other baseline characteristics will be presented by means of descriptive statistics

### 10.1.2 Covariates and prognostic variables

No consideration to any covariates or prognostic factors will be taken in the statistical analysis.

### 10.1.3 Handling of dropouts and missing data

Subjects dropping out from the study during the recruitment period will be replaced. Subjects dropping out after completion of the recruitment period will not be replaced but compensated for in the sample size estimation, see Section 10.4 Determination of sample size. Dropouts will be analyzed as described in Section 10.2 Description of analysis sets.

### 10.1.4 Multi-center

This study is a multi-center study. However, there is no a priori reason to suspect that there will be any qualitative differences between the study sites regarding any of the efficacy variables nor regarding the safety variables. Therefore the primary statistical analysis will not include study sites in the model but the result of the primary variable will as well be presented by study site.

## 10.2 Description of analysis sets

The study will be analyzed using a Safety (S) and a Per Protocol (PP) population approach. The S analysis set will consist of all enrolled subjects where any safety parameters, study specific procedures or study specific measures were performed and/or collected. Safety events will be divided and presented as two different groups depending on when the safety event started:

- 1. Pre-Permanent Restoration delivery: Safety events with start date prior to Permanent Restoration i.e. the period from Implant installation up to Permanent Restoration delivery date.
- 2. Post permanent delivery: Safety events with start date same as or after Permanent Restoration delivery i.e. Permanent Restoration delivery until end of study.

The PP analysis set will consist of all subjects fulfilling the inclusion criteria, none of the exclusion criteria and have been treated in accordance with the CIP, e.g. have an implant placed and the final permanent restoration within six months after implant placement, according to Acuris-conometric concept. Treatment efficacy related conclusions will be based on the results from the PP analysis.

All subject data will be included in subject data listings.

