#### **Exclusion criteria**

Any of the following is regarded as a criterion for exclusion from the study (all criteria applies at study inclusion, but criteria numbered 1-5 also applies during the entire study period):

- 1. Unlikely to be able to comply with study procedures, according to Investigators judgement
- 2. Subject is not willing to participate in the study or not able to understand the content of the study
- 3. Unable or unwilling to return for follow-up visits for a period of five years
- 4. Involvement in the planning and conduct of the study
- 5. Simultaneous participation in another clinical study, or former participation in a clinical study during the last 6 months that may interfere with the present study
- 6. Previous enrolment in the present study
- 7. Severe non-compliance to CIP as judged by the Investigator and/or Dentsply Sirona Implants.
- 8. Uncontrolled pathological process in the oral cavity
- 9. Known or suspected current malignancy
- 10. History of radiation therapy in the head and neck region within 12 months prior to surgery
- 11. Systemic or local disease or condition that could compromise post-operative healing and/or osseointegration
- 12. Uncontrolled diabetes mellitus
- 13. Corticosteroids, iv bisphosphonates or any other medication that could influence postoperative healing and/or osseointegration
- 14. Current need for major bone grafting and/or augmentation in the planned implant area (minor grafting and soft tissue grafting are allowed)
- 15. Present alcohol and drug abuse
- 16. Smoking more than 10 cigarettes per day

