#### 5.3.3.2 Exclusion criteria

Any of the following is regarded as a criterion for exclusion from the study (all criteria applies at study inclusion, but criteria numbered 1-5 also applies during the entire study period):

- 1. Unlikely to be able to comply with study procedures, according to Investigators judgement
- 2. Subject is not willing to participate in the study or not able to understand the content of the study
- 3. Involvement in the planning and conduct of the study
- 4. Severe non-compliance to CIP as judged by the Investigator and/or Dentsply Sirona Implants.
- 5. Unable or unwilling to return for follow-up visits for a period of five years
- 6. Simultaneous participation in another clinical study, or former participation in a clinical study during the last 6 months that may interfere with the present study
- 7. Previous enrolment in the present study
- 8. Uncontrolled pathological process in the oral cavity
- 9. Known or suspected current malignancy
- 10. History of radiation therapy in the head and neck region within 12 months prior to surgery
- 11. Systemic or local disease or condition that could compromise post-operative healing and/or osseointegration
- 12. Uncontrolled diabetes mellitus

- 13. Corticosteroids, iv bisphosphonates or any other medication that could influence postoperative healing and/or osseointegration
- 14. Current need for major bone grafting and/or augmentation in the planned implant area (minor grafting and soft tissue grafting are allowed)
- 15. Present alcohol and drug abuse
- 16. Smoking more than 10 cigarettes per day

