# 5.5.3 Procedure for handling enrolled subjects that fail to fulfill inclusion/ exclusion criteria

If a subject has been enrolled, but no study-related surgical procedures were performed (withdrawal of consent, not meeting all pre-surgical criteria etc.) the Investigator must document this in the subject records. The subject should be discontinued and no follow-up is necessary from a study perspective.

If a subject has been enrolled and study-related surgery started, but for any reason no Investigational Product (IP) could be inserted (e.g. not enough bone according to inclusion/exclusion criteria), the Investigator must document this in the subject records. The subject should be discontinued and no follow-up is necessary from a study perspective. However the subject should be treated according to standard practice.

If a subject has been enrolled and received the IP, although the inclusion/ exclusion criteria are violated, the subject will continue in the study, but will not be part of the Per Protocol (PP) analysis.

If a subject will not receive the permanent restoration within 6 months after implant placement, the subject will discontinue the study (not eligible according to Inclusion criteria no. 17) and no follow-up is necessary from a study perspective.

• If a subject lose the study implant (implant failure) before the permanent restoration is in place, the subject will discontinue the study and no follow-up is necessary from a study perspective.

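### The plan conflicts on when Per Protocol membership is settled; read literally, a subject with an observed prosthetic failure who then leaves drops out of the only efficacy set

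*Combined protocol and SAP*

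**What the plan says.** Section 10.2 sets up two analysis sets, Safety and PP, and rests efficacy conclusions on PP. Its definition begins: "The PP analysis set will consist of all subjects fulfilling the inclusion criteria, none of the exclusion criteria". It also requires treatment in line with the plan, and illustrates this with implant placement and a permanent restoration within six months.

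Section 5.3.3.2 states that "criteria numbered 1-5 also applies during the entire study period". In that list, numbers 1-5 include:
- no. 2: "Subject is not willing to participate in the study or not able to understand the content of the study"
- no. 4: "Severe non-compliance to CIP as judged by the Investigator and/or Dentsply Sirona Implants"
- no. 5: "Unable or unwilling to return for follow-up visits for a period of five years"

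The synopsis numbers the same criteria differently. There the non-compliance item reads "7. Severe non-compliance to CIP as judged by the Investigator and/or Dentsply Sirona Implants", which puts it outside 1-5, and simultaneous participation in another study moves inside. Unwillingness and non-return fall within 1-5 in both lists.

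Section 5.5.3 says that a subject who received the product although criteria were violated stays in the study but "will not be part of the Per Protocol (PP) analysis". Section 7.5 says that the further handling of deviations, "with special focus on the effect on the data analysis is described in section 10.2 Description of analysis sets". Section 10.1.3 likewise refers dropouts to 10.2. Section 10.2 contains neither a dropout rule nor a deviation procedure.

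Appendix B schedules the inclusion/exclusion check at Visits 1, 2 and 5, and at none of the follow-up visits 6-11.

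**The concern.** Take a subject restored on time who loses conometric retention at month 5. Section 6.3.1.2 makes this a *No* on the primary variable. If the subject then withdraws or stops returning, an exclusion criterion that runs for the whole study is met. The PP definition admits only subjects who meet none, so the failure leaves the primary analysis. Under the 5.3.3.2 numbering, a later finding of severe non-compliance has the same effect, and the investigator or sponsor may make that judgement with the outcome already known. Section 5.2 lets non-compliant subjects continue, so a failure can be observed in someone outside PP.

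The study has one arm and tests against a fixed 90%, so no control group shares the distortion. If subjects with a failed prosthesis leave PP more readily than others, survival is overstated and the test can exceed its 2.5% level. No second efficacy set would show the difference.

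**Working it through.** **Inputs.** From 10.3.1 and 10.4: null survival 90%, expected survival 97%, exact binomial test, level 0.025, 133 evaluable, 15% drop-out, 157 to be included. The documents give no departure rate specific to failures; the values below are assumptions.

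**The plan's own figure.** With 0.025 taken as one-sided:

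n = [(1.9600·√(0.90·0.10) + 1.2816·√(0.97·0.03)) / 0.07]² = 132.8, rounded up to 133; 133/0.85 = 156.5, rounded up to 157.

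Both reproduce. At n = 133 the exact test rejects with at most 6 failures: actual level 0.0172, power 0.894.

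**Model for departures.** Let π be true 1-year survival, f_S the share of non-failures leaving PP and f_F the share of failures leaving PP. The proportions kept are

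a = π(1 − f_S) for non-failures and b = (1 − π)(1 − f_F) for failures.

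Apparent survival is a/(a + b). The number in PP is binomial with N = 157 and probability a + b. The chance of rejection averages the exact test over that number, with the critical value recomputed for each size. Here f_S = 0.15, the plan's drop-out rate. Taking all 157 as restored is a simplification, since some will leave before Visit 5.

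For example, with π = 0.90 and f_F = 0.30: a = 0.765, b = 0.070, a/(a + b) = 0.765/0.835 = 0.9162.

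| π | f_F | Apparent survival | Chance of rejecting |
|---|---|---|---|
| 0.90 | 0.15 | 90.0% | 1.7% |
| 0.90 | 0.20 | 90.5% | 2.7% |
| 0.90 | 0.25 | 91.1% | 4.2% |
| 0.90 | 0.30 | 91.6% | 6.4% |
| 0.97 | 0.15 | 97.0% | 89.0% |
| 0.97 | 0.30 | 97.5% | 94.8% |

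At 97%, 157 × 0.03 = 4.7 failures are expected. Raising f_F from 0.15 to 0.30 removes a further 4.7 × 0.15 = 0.7 of a subject.

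**One subject at the cutoff.** Seven failures in 134 give one-sided p = 0.036 and an exact 95% lower limit of 89.5%: not rejected. If one of the seven leaves PP, six in 133 give p = 0.017 and a lower limit of 90.4%: rejected.

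**The opposite error.** Keeping every failure (f_F = 0) while dropping 15% of event-free subjects gives, at π = 0.97, 0.8245/(0.8245 + 0.0300) = 96.5% apparent survival and 80.8% power.

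**The case against.** The best defence is that eligibility is meant to be settled by Visit 5. Appendix B has no criteria check after that visit. The one late criterion, no. 17, applies at Visit 5. The illustration in 10.2 stops at the restoration. Section 5.5.3 most naturally concerns violations already present when the product was received. Section 5.5.1 lists withdrawal, loss to follow-up and severe non-compliance separately from incorrect enrollment, so the whole-study wording in 5.3.3.2 may govern continued participation rather than PP membership. This carries weight: a reader might infer that the plan definitely removes later leavers from PP, and the documents do not go that far. But the illustration in 10.2 qualifies treatment according to the plan, not the separate condition on exclusion criteria, and no sentence limits that condition to Visit 5.

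Failures also remain visible. Section 6.4.2 gives loss of retention and abutment loss or fracture as examples of adverse device effects, and all data are listed. That is true, but neither enters the primary test.

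Three further inferences are tempting and lack support:
- **Much larger inflation.** If 40-50% of failures left PP, the error would be far higher, but nothing in the documents supports such rates.
- **Discontinued failures are lost as a class.** Subjects discontinued for implant loss or component replacement who remain willing and compliant meet none of these criteria. Sections 6.3.1.2, 10.2 and 10.3.1 point to keeping them.
- **Departures in years 2-5 cost the 1-year test its power.** Section 10.5 declares a partial clean file once all subjects have completed Visit 7, and nothing says that the 1-year test is rerun on a later, smaller set. A low figure such as 74.8% power at n = 113 is also mostly an effect of the discrete cutoff, since n = 114 gives 87.1%.

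**Conclusion.** The concern holds as a conflict in the text. Sections 10.2 and 5.3.3.2 read together let an observed failure leave the only efficacy denominator; Appendix B suggests that membership closes at Visit 5; the two numberings disagree on whether later severe non-compliance counts. Neither 7.5 nor 10.1.3 resolves it.

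The size depends on unequal departure. If leaving PP is unrelated to failure, there is no bias and the error stays at 1.7%. On the assumed range of 20% to 30% of failures leaving, against 15% of non-failures, it is 2.7% to 6.4% at a true survival of 90%. At the plan's expected 97% the estimate moves by about half a percentage point. The practical exposure is a result near the cutoff, where one subject can reverse the conclusion. This is a cheap improvement to make before the data are analysed, not evidence that the result will be wrong.

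**What to change.** In 10.2, state that:
1. PP membership is fixed at Visit 5, using the criteria as met at inclusion plus no. 17. Later withdrawal, non-return or non-compliance does not remove a subject.
2. A PP subject who meets a *No* criterion of 6.3.1.2 by Visit 7 counts as *No*, discontinued or not. This applies only where such a criterion is met, not to every component replacement.
3. One named rule covers subjects who leave event-free before Visit 7. It must not simply drop them while all failures are kept, because that biases the estimate downwards as shown above. A Kaplan-Meier 1-year estimate is an optional way to use their time at risk.

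Reconcile the criteria numbering between the synopsis and 5.3.3.2. The content of the exclusion and discontinuation rules stays with the sponsor.

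The cost is a few sentences and a numbering correction. No new data are needed, since failures are already captured as adverse device effects and discontinuations resulting from them are recorded on the termination page. The downside is that the set will include subjects who later became non-compliant; the stricter set can be shown as a sensitivity analysis.
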